5.3 DATA COLLECTED FROM WITHDRAWN SUBJECTS

Every attempt should be made to collect follow-up information. The reason for withdrawal from the study will be recorded in the source documents and on the appropriate page of the CRF.

Before a subject is identified as lost-to-follow up, the site should make all reasonable efforts to contact the subject. These attempts must be documented and should include at a minimum one phone call and one certified letter.

In the event that a subject is withdrawn from the study at any time due to an adverse event or SAE, the procedures stated in [Sections 9.2](#) and [9.4](#) must be followed.

5.4 SCREEN FAILURES

A subject who signed a consent form, but did not meet the inclusion/exclusion criteria is classified as a screen failure. Subject number, demographics and reason for screen failure will be recorded.

In the event that a subject initially fails to meet inclusion/exclusion criteria and is later reconsidered for participation, will be re-consented and assigned a new unique identification number at the time of re-screening. Subjects who fail their first screening attempt may be re-screened again (i.e., up to two screenings) and may be enrolled if they are found to meet all inclusion and no exclusion criteria at the subsequent screening visit.

6 STUDY TREATMENT

Eligible subjects will receive the combination leronlimab (PRO 140) and carboplatin. Leronlimab (PRO 140) will be administered weekly at a dose assigned at time of enrollment and carboplatin target of AUC 5 every 3 weeks as combination therapy until disease progression or intolerable toxicity.

Table 6-1: Treatment Administration Summary

Study Drug	Premedication	Dose	Route	Schedule	Cycle Length	Supportive Therapies
Leronlimab (PRO 140)	N/A	Assigned dose cohort*	SC	Start on Day 1 and every week thereafter	N/A	N/A
Carboplatin	Antiemetics	AUC 5	IV Infusion	Day 1 every 3 weeks (21 Days)	3 weeks (21 Days)	Omeprazole or similar agents, ondansetron or similar antiemetics

*Phase Ib: Cohort A: 350 mg PRO 140 SC weekly; Cohort B: 525 mg PRO 140 SC weekly; Cohort C: 700 mg PRO 140 SC weekly

*Phase II: MTD PRO 140 SC weekly

Supportive care: Any required supportive care treatment such as antibiotics, anti- emetics, proton pump inhibitors and others will be given per institutional standards.

6.1 LERONLIMAB (PRO 140)

Leronlimab (PRO 140) is a humanized IgG4,κ monoclonal antibody (mAb) to the chemokine receptor CCR5. Leronlimab (PRO 140) is provided at a concentration of 175 mg/mL and is intended for SC route of administration.

A total of 350 mg or 525 mg or 700 mg of leronlimab (PRO 140) (175 mg/mL) is delivered as two injections administered subcutaneously on opposite sides of the abdomen.

- Leronlimab (PRO 140) 350 mg dose will be administered as two injections of 1 mL each.
- Leronlimab (PRO 140) 525 mg dose will be administered as two injections of 1.5 mL each.
- Leronlimab (PRO 140) 700 mg dose will be administered as two injections of 2 mL each.

One study injection kit will be assigned per subject per treatment visit. Kits will be labeled with a unique identification number. Each kit used during the Treatment Period will contain two, three or four vials of leronlimab (PRO 140) for SC injection.

Each vial of the leronlimab (PRO 140) product contains ~1.4 mL antibody at 175mg/mL in a buffer containing 5 mM L-histidine, 15.0 mM glycine, 95 mM sodium chloride, 0.3% (w/v) sorbitol, 0.005% (w/v) polysorbate 20 (Tween 20®), and sterile water for injection, at pH of 5.5.

Note: 1 mL will be drawn from 1.4 mL solution in a vial. Remaining 0.4 mL medication will be discarded appropriately from each vial.

Table 6-2: Investigational Product - leronlimab (PRO 140)

IP Dosage	Dosage Form	IP concentration	Dosing Frequency and Amount	Route of Administration
PRO 140 350mg	Parenteral solution	175 mg/mL	2 injections of PRO 140 (1 mL/inj.) per week on opposite sides of abdomen	SC injection
PRO 140 525 mg	Parenteral solution	175 mg/mL	2 injections of PRO 140 (1.5 mL/inj.) per week on opposite sides of abdomen	SC injection
PRO 140 700 mg	Parenteral solution	175 mg/mL	2 injections of PRO 140 (2 mL/inj.) per week on opposite sides of abdomen	SC injection

Note: Patients with low body fat percentages may find subcutaneous injections uncomfortable esp. in case of 1.5 mL or 2mL injection for the 525 mg or 700mg dosing, respectively. In such cases, leronlimab (PRO 140) 525 mg can be injected as three 175mg/ml injections, or leronlimab (PRO 140) 700 mg can be injected as four 175mg/ml injections and/or subcutaneous injections can be placed at different areas other than abdomen as per discretion of the Investigator.

6.1.1. Leronlimab (PRO 140) - Packaging and Labeling

Study drug will be prepared by Ajinomoto Althea, Inc. and will be packaged, labeled, and shipped by Sherpa Clinical Packaging, LLC.

The contents of each vial are described in [Section 6.1](#). Leronlimab (PRO 140) kits will be labeled with information such as: study protocol #; fill volume; concentration; storage condition; a “use as per study protocol” statement; a cautionary statement; sponsor’s name and address; and the kit number.

Below are representative samples of the Investigational Product, FDP individual vial ([Figure 6-1](#)), syringe label ([Figure 6-2](#)), and kit labels ([Figure 6-3](#)) designated for use in this clinical protocol. Each kit contains two labeled vials and two syringe labels.

Figure 6-1: Investigational Product - Vial Label

Protocol: PRO 140_CD07 Subject No. _____ Single use 3 mL vial contains 1.4 mL of PRO 140 (175 mg/mL) solution for subcutaneous injection Store at 2°C to 8°C (36°F to 46°F) USE AS PER STUDY PROTOCOL Caution: New Drug – Limited by Federal (or United States) Law to Investigational Use CytoDyn Inc., Vancouver, WA, USA	Kit No. xxx	Protocol: PRO 140_CD07 Subject No. _____ Single use 3 mL vial contains 1.4 mL of PRO 140 (175 mg/mL) solution for subcutaneous injection Store at 2°C to 8°C (36°F to 46°F) USE AS PER STUDY PROTOCOL Caution: New Drug – Limited by Federal (or United States) Law to Investigational Use CytoDyn Inc., Vancouver, WA, USA	Kit No. xxx
---	-------------	---	-------------

Figure 6-2: Investigational Product - Syringe Label

Protocol: PRO 140_CD07	Contents of Kit No. xxx
This syringe contains 1/1.5/2 mL PRO 140 (175 mg/mL) solution for subcutaneous injection	
USE AS PER STUDY PROTOCOL	
Caution: New Drug – Limited by Federal (or United States) Law to Investigational Use	
CytoDyn Inc., Vancouver, WA, USA	

Figure 6-3: Investigational Product - Kit Label

Protocol: PRO 140_CD07	Kit No. xxx
Site No. _____	Subject No. _____
This kit contains 2/3/4 single-use vials	
Each 3 mL vial contains 1.4 mL of PRO 140 (175 mg/mL) solution for subcutaneous injection	
Store at 2°C to 8°C (36°F to 46°F)	
USE AS PER STUDY PROTOCOL	
Caution: New Drug – Limited by Federal (or United States) Law to Investigational Use	
CytoDyn Inc., Vancouver, WA, USA	

The pharmacy manual provides the criteria regarding vial acceptance or rejection, as well as instructions for the preparation of the IP syringes to be used to administer drug.

6.1.2. Leronlimab (PRO 140) - Storage and Handling

Study drug will be shipped at 2°C to 8°C (refrigerated [36°F to 46°F]) to the investigator's site. Upon receipt at the site, the responsible site staff or pharmacist should verify the integrity of the vials. Study drug should be stored at 2°C to 8°C (refrigerated [36°F to 46°F]). The contents of the vial should appear as a clear to opalescent, colorless to yellow solution; fine translucent particles may be present. This is normal.

The investigator must maintain an accurate record of the shipment, storage, and dispensing of the study drug in a drug accountability log. An accurate record including the date and amount of study drug dispensed to each subject must be available for inspection at any time. A study CRA assigned

to monitor the investigational site will review these documents once study drug has been received by the investigational site. Study drug will be accounted for on an ongoing basis during the study.

6.1.3. Leronlimab (PRO 140) - Administration

Guidelines for dose preparation can be found in the pharmacy manual.

Leronlimab (PRO 140) will be provided to the administering personnel in single-use syringes prepared from vials of study drug stored at 2-8°C at the site pharmacy prior to use. Each of two syringes is filled to deliver 1.0, 1.5 or 2 mL of study drug (per assigned dose).

Equivalent volumes of PRO 140 will be administered subcutaneously on opposite sides of the abdomen.

A 21-gauge needle should be used to remove PRO 140 from vial and a 25-gauge needle is used for administration to subjects.

IP should be administered slowly over 15 seconds per mL. Leronlimab (PRO 140) should not be kept in syringe for longer than 60 minutes.

Following each SC delivery of drug, careful examination will be made to assess the appearance of any study drug Injection Site Reactions (ISRs) as per CTCAE v5.0

All doses of study drug will be prepared by either the credentialed pharmacist or qualified medical professional and will be administered as SC injection by a licensed medical professional when leronlimab (PRO 140) is administered at clinic site. Self administration by subjects at home is allowed at certain visits.

All leronlimab (PRO 140) SC weekly injections at Cycle 1 (Days 1, 8, and 15) and at Day 1 of subsequent cycles must be administered at clinic. The remaining study treatment injections at Day 8 and Day 15 (beyond Cycle 1) may be self-administered by subjects at home after proper training by a healthcare professional.

Note: It is preferred that the same injection site be used throughout the study. At the same time, it is not recommended to inject the study drug into areas where skin shows signs of a previous injection site reaction. It is advised to change the injection site if any previous injection site reaction remains unresolved.

6.1.4. Leronlimab (PRO 140) - Post Injection Monitoring

Subject will be observed at approximately 30 minutes post-injection or longer if necessary for injection site reaction as per CTCAE v5.0.

In addition, the tolerability of repeated subcutaneous administration of PRO 140 is evaluated based on assessment of subject-perceived injection site pain using the Pain Visual Analog Scale (VAS).

6.1.5. Leronlimab (PRO 140) - Dose Modifications

The dose interruption, reduction, and permanent discontinuation for any toxicity are described below.

Dose interruption: Refer to [Table 6-3](#) below. Recovery to acceptable levels must occur to allow leronlimab (PRO 140) continuation. Any adverse event deemed to be related to leronlimab (PRO 140) that requires a dose hold of more than 21 days will result in permanent discontinuation of leronlimab (PRO 140).

Table 6-3: Leronlimab (PRO 140) Dose Modification and Management for Injection Site Reactions

CTCAE Grade	Treatment Modifications
Grade 1	No dose adjustment is required.
Grade 2	First Occurrence: No dose adjustment is required. Second Occurrence of the same event: Closely follow-up for resolution of the AE to Grade ≤ 1
Grade 3	Withhold treatment until symptoms resolve to: • Grade 1 or less
Grade 4	Study treatment will be permanently discontinued
Dose Limiting Toxicities (DLT) as outlined under Section 3 (Study Design)	Study treatment will be permanently discontinued

Note:

- *If Grade 3 event meets the DLT criteria: Study treatment will be permanently discontinued*
- *If Grade 3 event does not meet the DLT criteria: Study treatment will be withheld until symptoms resolve to Grade 1 or less before administering the next dose.*

Dose Modification: If a dose-response relationship for toxicity is observed, a reduced dose can be given to the subject. Dose adjustments will be allowed based on the toxicity, efficacy evaluation, and clinical judgment by physician.

- **Cohort B (PRO 140 525 mg):**

Dose de-escalation: If a dose-response relationship for toxicity is observed at leronlimab (PRO 140) 525 mg dose, the dose can be de-escalated to 350 mg. If no toxicity is observed at reduced dose (350 mg), the subjects will receive the reduced dose until disease progression, consent withdraw or death. No more dose de-escalation will be allowed if another toxicity event is observed at reduced dose level.

- **Cohort C (PRO 140 700 mg):**

Dose de-escalation: If a dose-response relationship for toxicity is observed at leronlimab (PRO 140) 700 mg dose, the dose can be de-escalated to 525 mg. If no toxicity is observed at reduced dose (525 mg), the subjects will receive the reduced dose until disease progression, consent withdraw or death. One more dose de-escalation (to 350 mg) will be allowed as per discretion of the treating physician.

Permanent discontinuation of Treatment: If Dose Limiting Toxicity (DLT) is reported at 350mg dose.

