6.2.13. Carboplatin - Toxicity Management & Dose Delays/Modifications

The dose interruption, reduction, and permanent discontinuation for any toxicity are described below.

Dose interruption: Refer to table below. Recovery to acceptable levels must occur to allow carboplatin continuation.

Table 6-4: Carboplatin Dose Modification and Management

Toxicity	Grade/Description	Carboplatin
Hematologic Toxicities		
Thrombocytopenia	Grade 1	Maintain dose level.
	Grade 2	Hold dose & follow CBC weekly. Once \leq Grade 1 (platelets \geq 75,000/mm ³), resume at same dose.
	Grade 3	Dose reduction to AUC 4
	Grade 4	Permanently discontinue Carboplatin
Neutropenia	Grade 1 , 2 or 3 without fever	Maintain dose level.
	Grade 3 w/ fever or Grade 4	1st occurrence: Hold dose & follow CBC weekly. Once resolved to $> 1.0 \times 10^9/L$ (if neutropenia was the only toxicity noted), resume at same dose. If other toxicity was noted, resume with AUC 4. 2nd occurrence: Discontinue Carboplatin
Non-Hematologic Toxicities		
Allergic reaction or hypersensitivity	\leq Grade 3	Hold dose until resolved to \leq Grade 1 & then resume at same dose level.
	Grade 4	Permanently discontinue Carboplatin

Toxicity	Grade/Description	Carboplatin
Infection	Grade 1 or 2	Hold dose until systemic treatment for infection is complete. If no neutropenia, resume at same dose level. If neutropenic, follow instructions above (hematologic section). If no resolution after > 3 weeks: permanently discontinue Carboplatin
	Grade 3	Discontinue Carboplatin
Herpes zoster or simplex	Any grade	Hold dose until lesions are dry & then resume at same dose level.
Neuropathy	Grade 2 w/pain or Grade 3	Hold dose until resolved to \leq Grade 2 or baseline then resume at AUC 4. May continue on single-agent leronlimab (PRO 140) (per treating investigator's discretion)
	Grade 4	Permanently discontinue Carboplatin
Renal dysfunction	CrCl \leq 15 mL/min	Hold dose until CrCl $>$ 15 mL/min & then resume.

Note: Patients who discontinue carboplatin for any reason will be allowed to continue to receive leronlimab (PRO 140) per treating investigator's discretion. In such cases, patients will be re-consented so that they are appropriately informed of other treatment options that have demonstrated improvement in clinical outcomes.

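### The rules for stopping leronlimab after a dose-limiting toxicity do not agree: Table 6-3, the 350 mg rule, the de-escalation text and the note to Table 6-4 can give different answers for the same patient (minor)

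*Protocol*

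**What the plan says.** Four texts govern what happens to leronlimab after a DLT.

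- **Table 6-3, last row (Section 6.1.5).** The table is titled "Leronlimab (PRO 140) Dose Modification and Management for Injection Site Reactions". Its last row covers "Dose Limiting Toxicities (DLT) as outlined under Section 3 (Study Design" and the action is a permanent stop of study treatment. No dose is named, and item c of the Section 3 list (the injection-site DLT) is not singled out. A note adds: "If Grade 3 event meets the DLT criteria: Study treatment will be permanently discontinued".
- **De-escalation text (Section 6.1.5).** For Cohort C: "If a dose-response relationship for toxicity is observed at leronlimab (PRO 140) 700 mg dose, the dose can be de-escalated to 525 mg". A parallel paragraph allows 525 mg to go to 350 mg.
- **Last line of Section 6.1.5.** "Permanent discontinuation of Treatment: If Dose Limiting Toxicity (DLT) is reported at 350mg dose". It stands outside the table and is not limited to one type of DLT.
- **Table 6-4 and its note (Section 6.2.13).** For Grade 4 thrombocytopenia: "Permanently discontinue Carboplatin". The note says: "Patients who discontinue carboplatin for any reason will be allowed to continue to receive leronlimab (PRO 140) per treating investigator's discretion". Re-consent is required. The note has no exception for an event that is also a DLT.

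On scope, Section 6.1.5 opens with "The dose interruption, reduction, and permanent discontinuation for any toxicity are described below", and Section 7.10 also sends sites to Tables 6-3 and 6-4 for toxicity of any kind. Section 3, item j, counts Grade 4 thrombocytopenia lasting more than 7 days as a DLT. Unlike items a and d to g, it does not require attribution to leronlimab.

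**The concern.** A site with a DLT in front of it needs one answer on whether leronlimab stops, may be reduced, or may continue alone. These texts supply different answers without saying which takes precedence. The clearest case is foreseeable: Section 6.2.10 lists thrombocytopenia as carboplatin's dose-limiting effect. These are safety stopping rules, and with up to five centers (Section 3.1) two sites could handle the same event differently and each cite the protocol.

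The term study treatment adds to the uncertainty. Section 6, under that heading, covers both drugs, while Table 6-3 is a leronlimab table. It is not clear whether the row stops leronlimab, carboplatin or both.

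**Working it through.** The plan gives no figure to reproduce. The check traces one patient through the texts and then sizes the exposure.

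**Trace.** A Phase Ib patient has Grade 4 thrombocytopenia lasting more than 7 days in Cycle 1. Item j makes it a DLT, and Table 6-4 stops carboplatin. For leronlimab:

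| Dose | Table 6-3 row, if all Section 3 DLTs | Table 6-3 row, if item c only | Last line of 6.1.5 | De-escalation text | Table 6-4 note |
|---|---|---|---|---|---|
| 350 mg | stop | silent | stop | no lower dose | may continue |
| 525 or 700 mg | stop | silent | silent | lower dose possible if a dose-response relationship is seen | may continue |

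At 350 mg the last line of 6.1.5 and the note differ whichever way the row is read. At 525 or 700 mg the divergence depends on the row's scope.

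**Size.** The documents give no event rates, so these are assumptions: total DLT rate p per patient of 5% to 20%, the same at each dose, including item j thrombocytopenia at rate q of 1% (with p = 5%) to 5% (with p = 20%). The 3+3 rule is taken from Section 3: 0 of 3 or 1 of 6 escalates, two or more stops, and the MTD is filled to six.

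*At 350 mg.* The chance that a dose is passed is s = (1−p)³ + 3p(1−p)² × (1−p)³.
- p = 5%: s = 0.857 + 0.135 × 0.857 = 0.973.
- p = 20%: s = 0.512 + 0.384 × 0.512 = 0.709.

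Expected patients at 350 mg = 3 + 3 × 3p(1−p)² + 3 × (1−p)³ × (1−s). The second term is the expansion after one DLT. The third is filling 350 mg to six when 525 mg fails.
- p = 5%: 3 + 0.406 + 0.068 = 3.47. With q = 1%: 3.47 × 0.01 = 0.035 patients.
- p = 20%: 3 + 1.152 + 0.448 = 4.60. With q = 5%: 4.60 × 0.05 = 0.23 patients.

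*All doses.* Simulating the same rule gives mean enrollment of 12.5 (p = 5%) and 10.7 (p = 20%).
- 12.5 × 0.01 = 0.125, about 0.13 patients; chance of at least one about 12%.
- 10.7 × 0.05 = 0.535, about 0.54 patients; chance of at least one about 44%.
- Ceiling with all 18 enrolled: 18 × 0.01 = 0.18 to 18 × 0.05 = 0.90.

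*Any DLT at 525 or 700 mg,* where the row and the de-escalation text might both seem to apply: about 0.46 to 1.2 patients, with a 36% to 61% chance of at least one. This is an upper bound. It counts deaths and anaphylaxis, where de-escalation is no real choice, and DLTs without a dose-response relationship.

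**The case against.** The strongest reply is that this is ambiguity, not contradiction, and much of that stands.

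- **The row may mean injection-site DLTs only.** The table title, the wording of item c and the parallel rules in Section 9.2.6 all support this. Against it, the row cites Section 3 without limit, and Sections 6.1.5 and 7.10 both speak of toxicity in general. The narrow reading also leaves the row almost nothing to do, since the Grade 4 row and the note on Grade 3 events already cover item c. It would leave 6.1.5 with no explicit stop for a DLT such as anaphylaxis at 525 or 700 mg. In any case it does not remove the divergence at 350 mg.
- **The Table 6-4 note is permissive.** It can be read as saying only that stopping carboplatin does not by itself require stopping leronlimab, so that a mandatory stop in 6.1.5 still governs. A site can obey both texts by stopping leronlimab. A reader might infer a flat contradiction; the documents do not support that. What remains is that the note does not say it is subordinate.
- **The de-escalation text can be reconciled.** It speaks of toxicity and does not mention DLTs, so it can be taken to cover non-DLT toxicity only. The 350 mg line does not say that only a DLT at that dose stops treatment. A reader might infer that the protocol permits re-dosing at a lower dose after any DLT at 525 or 700 mg, even anaphylaxis or Hy's law; no text expressly permits that.
- **The event is hard to document in time.** Blood counts are scheduled at Screening, Day 1 of each cycle and end of treatment (Section 7.11), with none listed for Cycle 1 Days 8 and 15 (Section 4.3.2). The DLT window is 21 days (Section 8.5). Without an unscheduled count, a duration above 7 days would usually be established after the window closes. The exposure figures therefore probably run high.
- **Other safeguards exist.** The Medical Monitor reviews safety data before escalation, any listed DLT goes to the DSMB, and the treating physician may stop treatment in the patient's interest (Section 5.1). The DSMB review is directed at escalation, however, not at the individual patient's dosing.

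**Conclusion.** The point holds as an inconsistency in the leronlimab stopping rules, of minor severity. It does not depend on the scope of the Table 6-3 row: for a DLT such as item j thrombocytopenia at 350 mg, the last line of Section 6.1.5 stops treatment and the Table 6-4 note allows leronlimab to continue. If the row covers all Section 3 DLTs, the same divergence extends to 525 and 700 mg.

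The expected exposure is a fraction of one Phase Ib patient: 0.13 to 0.54 with item j overall and 0.035 to 0.23 at 350 mg, probably fewer given the blood-count schedule. These figures rest on assumed rates and an equal rate at each dose. DLTs are assessed in Cycle 1, and the documents do not say whether the row applies to the same events later or in Phase II.

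A reader might infer an effect on the MTD or on Phase II results. The documents do not support this: the event counts as a DLT under either handling, and nothing here touches power, sample size or PFS.

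**What to change.** 1. Add to the Table 6-4 note: *except where leronlimab must be permanently discontinued after a DLT under Section 6.1.5*. At minimum this covers any DLT at 350 mg.
2. Make the Table 6-3 DLT row and the last line of Section 6.1.5 state one rule. The default should be a permanent leronlimab stop for any Section 3 DLT in Phase Ib Cycle 1, at any dose, with the de-escalation paragraphs limited to toxicity that is not a DLT.
3. If the sponsor prefers to allow de-escalation after some DLTs at 525 or 700 mg, list them, and exclude anaphylaxis, Hy's law, life-threatening related events and Grade 4 injection-site reactions.
4. Define study treatment throughout Table 6-3 as leronlimab, carboplatin or both. Simply substituting leronlimab could remove a carboplatin stop without anyone deciding to.

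The cost is a minor amendment, which needs IRB approval under Section 11.3 because it changes what happens to patients. A few patients may lose the option of leronlimab alone. No extra patients, visits or tests are needed.

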9.2.6. Injection-site reactions

Injection-site reactions thought to be directly related to the injection are considered to be AEs of special interest, and will be assessed as per CTCAE v5.0.

For subjects who develop Grade 1 or Grade 2 events, therapy will be continued as per protocol. If a subject chooses to discontinue study treatment, the site should notify the protocol team leadership, and encourage the subject to complete any remaining study visits until the toxicity resolves.

For subjects who develop Grade 3 events following study drug injection, the subject should be reevaluated closely until the AE returns to Grade 1 or less, at which time study treatment may be reintroduced at the discretion of the site investigator. If the same Grade 3 AE recurs following the next administration of study drug, study treatment must be permanently discontinued. Subjects experiencing Grade 3 AEs requiring permanent discontinuation of study treatment should be followed closely for resolution of the AE to Grade 1 or less and the team leadership must be notified.

For Grade 4 events permanently discontinue therapy.

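### Protocol Section 6.1.5 gives stop rules for leronlimab that do not fit together after a non-fatal DLT at 525 or 700 mg

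*Protocol*

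**What the plan says.** Section 6.1.5 of the protocol opens with a wide scope: "The dose interruption, reduction, and permanent discontinuation for any toxicity are described below". It then gives three sets of instructions.

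- **Table 6-3 and its note.** The title confines the table to injection site reactions, but its last row has the trigger "Dose Limiting Toxicities (DLT) as outlined under Section 3 (Study Design", and the action is a permanent stop. The note below repeats this: "If Grade 3 event meets the DLT criteria: Study treatment will be permanently discontinued". Neither names a dose level.
- **The de-escalation paragraphs.** For Cohort B: "If a dose-response relationship for toxicity is observed at leronlimab (PRO 140) 525 mg dose, the dose can be de-escalated to 350 mg". For Cohort C: "If a dose-response relationship for toxicity is observed at leronlimab (PRO 140) 700 mg dose, the dose can be de-escalated to 525 mg", with a further step to 350 mg at the treating physician's discretion. Neither paragraph says whether a DLT counts as toxicity for this purpose.
- **The closing line.** Under its own label for permanent discontinuation, the section gives a single condition: "If Dose Limiting Toxicity (DLT) is reported at 350mg dose".

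Section 7.10 sends the reader to Section 3 for the DLT criteria, and to Tables 6-3 and 6-4 for managing toxicity of any kind from the two drugs.

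**The concern.** The line labelled as the permanent-discontinuation rule names only the lowest dose. Read straight after two paragraphs that allow step-down from 525 and 700 mg, it suggests that a DLT at a higher dose is handled by reduction and that only a DLT at 350 mg ends treatment. Table 6-3, in the same section, says that any Section 3 DLT ends treatment.

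After the same event, for example Hy's law at 700 mg, one site could stop leronlimab and another could give 525 mg, each citing Section 6.1.5. What is at stake is whether a patient who has had a serious toxicity is re-exposed to the drug. There is a smaller effect on the SAP 8.4.1 summary of adverse events leading to discontinuation. There is also one on whether continuing treatment is a deviation under Protocol 11.4.1, which lists failure to withdraw a patient who met withdrawal criteria.

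**Working it through.** The question is whether the text is consistent, so there is no plan figure to reproduce.

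**Step 1. The rules side by side, for a non-fatal DLT meeting Section 3 criteria.**

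| Dose at DLT | Table 6-3 and note | Cohort paragraph | Closing line | Agree? |
|---|---|---|---|---|
| 350 mg | Stop | None | Stop | Yes |
| 525 mg | Stop | May reduce to 350 mg | Not triggered | No |
| 700 mg | Stop | May reduce to 525 mg, then 350 mg | Not triggered | No |

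**Step 2. What the 350 mg qualifier does.** If every Section 3 DLT already ends treatment at every dose, naming 350 mg in the closing line adds nothing. It has a function only if a DLT at a higher dose may be managed by reduction. The wording therefore invites that reading, although it does not state it.

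**Step 3. Whether other text removes the difficulty.**

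- *Section 7.10* supports Table 6-3 as the governing rule, because it cites that table for toxicity generally. It leaves the closing line and the cohort paragraphs as they are.
- *Section 9.2.6* settles injection-site reactions at any dose. Grade 4 events stop therapy, and for Grade 3, "If the same Grade 3 AE recurs following the next administration of study drug, study treatment must be permanently discontinued". It does not reach other DLTs.
- *The 21-day limit on dose holds in Section 6.1.5* applies at any dose, but only to leronlimab-related events that need a hold longer than that.
- *Sections 4.3 and 5.1* let treatment end for unacceptable toxicity. That is clinical judgment and does not say that a DLT makes stopping mandatory.
- *DSMB review in Section 3* decides on escalation to the next cohort, not on what the affected patient receives next.
- *Sponsor review in Section 11.4* follows a deviation, and whether reduction after a DLT is a deviation is the open question.

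**Step 4. What is unaffected.** A DLT is counted when it occurs in Cycle 1. Later dosing of that patient does not alter the count, so the 3+3 decisions and the MTD stand under either reading.

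**Step 5. Size.** The Phase Ib maximum is 3 cohorts × 6 = 18 patients, of whom 2 × 6 = 12 would be in Cohorts B and C, before any replacement under Section 5.2. That is a ceiling on those enrolled at the two doses, not an expected number affected. The documents give no DLT rate for the combination. Section 1.4.3 reports no dose-limiting toxicities in earlier leronlimab trials, but those were mostly in healthy or HIV-positive subjects without carboplatin. No frequency can be derived.

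**The case against.** The strongest reply is that all the sentences can be obeyed together. Table 6-3 and its note are mandatory, whereas the cohort paragraphs are permissive and require toxicity that appears dose-related. The closing line says if, not only if, and can be read as ending the reduction ladder at its lowest rung. Section 7.10 points to Table 6-3. Stopping at every DLT breaches nothing, and no sentence requires treatment to continue after one.

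Most of this stands. It shows which rule should govern, and it rules out two stronger readings that a reader might infer: that the protocol requires leronlimab to continue after a DLT above 350 mg, and that nothing in the documents indicates a governing rule. It does not remove a stop line that names one dose, or step-down paragraphs that leave DLTs in.

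A second reply is that the Table 6-3 title limits it to injection site reactions. The section's opening sentence, the DLT row and Section 7.10 all point the other way. If the title did govern, most DLTs at 525 or 700 mg would have no explicit stop rule, which would be worse.

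A reader might also want to count the extra doses at stake by running treatment to the 5-month PFS given in Section 3. That figure is for newly recurred disease. The Phase Ib patients have progressed after up to two lines of metastatic therapy, so it does not transfer. Nor do the criteria divide cleanly into those covered elsewhere and those not: b, f and g can also meet rows of Table 6-4.

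**Conclusion.** The concern holds as an inconsistency by implication. For a non-fatal Section 3 DLT at 525 or 700 mg, Table 6-3 says stop, while the cohort paragraphs and the closing line can be read to allow reduction. The mandatory wording and Section 7.10 favour stopping, but a site could in good faith do otherwise. The consequence is for individual patient safety and later exposure. It would be wrong to infer that dose finding is compromised, because the DLT count, the escalation decisions and the MTD do not depend on it. How often it would matter cannot be estimated from the documents. The conclusion assumes that the Table 6-3 DLT row covers the whole Section 3 list, as its wording and Section 7.10 indicate.

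A related matter should be kept separate. For carboplatin-type DLTs (criteria i to k), Table 6-4 sets its own carboplatin actions, and its note says: "Patients who discontinue carboplatin for any reason will be allowed to continue to receive leronlimab (PRO 140) per treating investigator's discretion". Table 6-3 stops study treatment for the same events. The sponsor should state which table governs there.

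**What to change.** Align the text with the mandatory rule already in Table 6-3.

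1. Replace the closing line of Section 6.1.5 with: *Permanent discontinuation of leronlimab: if an event meeting the Section 3 DLT criteria (a to m) occurs at any dose level.*
2. In the Cohort B and Cohort C paragraphs, limit de-escalation by adding: *for toxicity not meeting the Section 3 DLT criteria.*
3. Keep the term study treatment in the Table 6-3 DLT row. Table 6-4 has no hepatic or electrolyte row, so narrowing that term to leronlimab would remove the only explicit DLT stop for carboplatin after Hy's law, a transaminase DLT or an electrolyte DLT.
4. State that a dose withheld for a Grade 3 injection-site reaction that does not itself meet the Section 3 criteria stays under Table 6-3 and Section 9.2.6, even where Section 5.2 counts the missed Cycle 1 dose as a DLT. The reference to criteria a to m in item 1 is there for this reason: a rule covering any DLT would turn a correctly withheld dose into a permanent stop.

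These are wording changes, with no effect on sample size, schedule or analysis. The clinical cost is that a patient with a manageable DLT at 525 or 700 mg, such as a Grade 3 electrolyte abnormality lasting more than 72 hours, could not continue leronlimab at a reduced dose. If the sponsor wants that option, it should say so and amend the Table 6-3 DLT row and note to match. Either way, the section should state one rule.
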